3.2.2.7 Time from externalized conductors to clinical intervention

Lead Population

All the leads with externalized conductors within the Riata, Riata ST silicone, QuickSite/QuickFlex (1056T, 1058T, 1156T, 1158), and Durata lead groups

Analysis:

Time to clinical intervention will be analyzed using the Kaplan-Meier method. The zero time will be the date at which externalized conductor was detected. Those patients who experience externalized conductor after enrollment but do not experience clinical intervention will be censored 3 years after enrollment in this trial. A separate Kaplan-Meier curve will be calculated for each of the lead subgroups outlined in Table 2.

For QuickSite/QuickFlex leads only, data from patients with an additional 1 year of follow-up will contribute to 2 separate lead subgroups (See Section 3.4.5).

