Assuming an annual mortality of 7% in the ICD patient population, the mortality at 3 years is 20% $[1 - (1-0.07)^3]$ In the recent RHYTHM ICD/QuickSite 1056K left heart lead study, the annual mortality was 12.8%, which would result in a mortality of 33.7% $[1 - (1-0.128)^3]$ at 3 years. If the ICD:CRT-D device mix is 60%:40% then the expected overall mortality in this study at 3 years is 25.5% ($=0.6 \times 0.20 + 0.4 \times 0.337$).

Withdrawals due to reasons other than death

In an ongoing St. Jude Medical post-approval study (SJ4 PAS), the attrition rate due to reasons other than death at 22 months of follow-up is 9%. Thus, it is anticipated that the attrition rate at 3 years for reasons other than death will be 15%.

Assuming that deaths and withdrawals are independent events, the total attrition is expected to be approximately 37% ($= 1 - (1-0.255) \times (1-0.15)$) over 3 years.

Since the Riata/Riata ST leads are recalled, it is more likely that some physicians will explant them, even when electrical function is normal. For this reason, an additional 10% of the patients are expected to be prematurely withdrawn. This leads to a total attrition of approximately 43% ($= 1 - (1-0.255) \times (1-0.15) \times (1-0.10)$) over 3 years.

Expected Attrition in patients with left ventricular leads
Withdrawals due to deaths

In the RHYTHM ICD/QuickSite 1056K left heart lead study, the annual mortality was 12.8%, providing an estimated mortality rate of 33.7 % $[1 - (1-0.128)^3]$ at 3 years.

Withdrawals for reasons other than death

In the ongoing St. Jude Medical post-approval study, the attrition rate due to reasons other than death at 22 months of follow-up is 9%. Thus, it is anticipated that the attrition rate at 3 years for reasons other than death will be 15%.

Assuming that deaths and withdrawals are independent events, the total attrition is expected to be approximately 43.6% ($= 1-(1-0.337) \times (1-0.15)$) over 3 years.

Table 2: Enrollment in Lead Subgroups

Lead Group	Age of Lead at Enrollment (Years)	Min Enrollment	Expected Attrition at 3 years*	Target Enrollment
Riata Silicone	≥ 7	100	47%	195
	≥ 6 and < 7	100	45%	185
	< 6	100	43%	180
Riata ST	≥ 5.5	100	45%	185
	< 5.5	100	43%	180
QuickSite 1056T/1058 and QuickFlex 1156T/1158T	≥ 6	115	46%	225
	≥ 5 and < 6	115	46%	225
	< 5	170	44%	300
Durata	≥ 5	167	37%	275
	≥ 4 and < 5	167	37%	275
	< 4	167	37%	275

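### Time to clinical intervention after an imaging finding is planned by Kaplan-Meier alone, with no rule for death, although death rules out intervention and 25.5% to 33.7% of patients are expected to die within 3 years

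*Combined protocol and SAP*

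**What the plan says.** Section 3.2.2.7 covers leads with externalized conductors: "Time to clinical intervention will be analyzed using the Kaplan-Meier method". The clock starts at detection: "The zero time will be the date at which externalized conductor was detected". One curve is drawn for each Table 2 subgroup. The only censoring rule is that patients who "do not experience clinical intervention will be censored 3 years after enrollment in this trial", and that sentence is written for findings that appear after enrollment. Section 3.2.2.8 repeats the design for other visual lead anomalies, by subcategory. Neither section mentions death, and no competing-risk or cumulative incidence method appears anywhere in the document.

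Mortality is planned for in section 3.1. For high-voltage leads, "the expected overall mortality in this study at 3 years is 25.5" percent. For left ventricular leads the cited study is described as "providing an estimated mortality rate of 33.7" percent at 3 years. Section 3.1 counts death as attrition, and section 9.0 lists it among the reasons for withdrawal.

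**The concern.** Death makes a later lead intervention impossible, so it is a competing event and differs in kind from loss to follow-up. Kaplan-Meier with deaths censored estimates how often intervention would occur if death were removed. A physician reading these curves is more likely to want the proportion of patients with an abnormal image who actually go on to an intervention. With a quarter to a third of patients expected to die within 3 years, the two quantities differ visibly.

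The written censoring rule adds a second problem. It can be read as stopping follow-up at death or as carrying every patient without an intervention to 3 years after enrollment. Two analysts following the same text could report different percentages from the same data.

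**Working it through.** **1. The plan's mortality figures (section 3.1).** The inputs are "Assuming an annual mortality of 7% in the ICD patient population, the mortality at 3 years is 20" percent; for the left ventricular lead study, "the annual mortality was 12.8" percent; and "If the ICD:CRT-D device mix is 60%:40" percent.
- ICD: 1 − 0.93³ = 19.6%, stated as 20%.
- Left ventricular: 1 − 0.872³ = 33.7%.
- Mix: 0.6 × 0.20 + 0.4 × 0.337 = 25.5% (25.2% if 19.6% is left unrounded).

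The stated figures reproduce.

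**2. Model.** Constant hazards over 3 years are assumed. K is the 3-year intervention risk with death removed, which is what 1 minus Kaplan-Meier estimates when deaths are censored at death. M is 3-year mortality.
- λ = −ln(1 − K)/3 and μ = −ln(1 − M)/3.
- Cumulative incidence = λ/(λ + μ) × [1 − (1 − K)(1 − M)].

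The documents give no intervention rate after an imaging finding, so K = 10% to 40% is an assumption. The only nearby figure is the extra 10% of Riata/Riata ST patients expected to leave because of explants (section 3.1), which is not specific to patients with a finding.

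Example with K = 20%, so λ = 0.0744:
- M = 25.5%: μ = 0.0981, and 0.0744/0.1725 × (1 − 0.80 × 0.745) = 0.431 × 0.404 = 17.4%.
- M = 33.7%: μ = 0.1370, and 0.0744/0.2114 × (1 − 0.80 × 0.663) = 0.352 × 0.470 = 16.5%.

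**3. Deaths censored at death, full 3 years.**

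| 1 − Kaplan-Meier | Cumulative incidence, 25.5% mortality | Excess (relative) | Cumulative incidence, 33.7% mortality | Excess (relative) |
|---|---|---|---|---|
| 10% | 8.7% | 1.3 points (15%) | 8.2% | 1.8 points (22%) |
| 20% | 17.4% | 2.6 points (15%) | 16.5% | 3.5 points (21%) |
| 30% | 26.2% | 3.8 points (14%) | 24.9% | 5.1 points (20%) |
| 40% | 35.1% | 4.9 points (14%) | 33.4% | 6.6 points (20%) |

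The relative excess hardly depends on the assumed K.

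**4. Shorter exposure.** Imaging is annual and the clock starts at detection. A finding first seen at 12 months has about 2 years left, and one seen at 24 months about 1 year. The relative excess falls to 9-10% (25.5% mortality) or 13-14% (33.7%) at 2 years, and to about 5% or 7% at 1 year.

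**5. Against sampling error.** The Riata subgroup aged 7 years or more has a target of 195 leads (Table 2). At the top of the reported range of externalization for Riata/Riata ST (0.5% to 33.3%, section 1.0), that gives 195 × 0.333 ≈ 65 leads. Other withdrawal is 15% over 3 years (section 3.1), so w = −ln(0.85)/3 = 0.0542. Greenwood variance = (1 − K)² × λ/[65(λ + μ + w)] × [exp(3(λ + μ + w)) − 1].
- K = 10%: standard error 4.2 points, excess 1.3 points, ratio 0.31.
- K = 40%: standard error 6.9 points, excess 4.9 points, ratio 0.71.

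Both use 25.5% mortality, the plan's figure for high-voltage leads.

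**6. Literal rule.** If everyone without an intervention stays at risk until 3 years, including patients who died or withdrew, the estimate becomes the raw observed proportion: λ/(λ + μ + w) × [1 − (1 − K)(1 − M)(0.85)]. At K = 20% this is 16.2% against a target of 17.4% (25.5% mortality), and 15.4% against 16.5% (33.7%). A simulation of 1,000,000 patients gave the same values. Keeping only the deaths at risk, with withdrawals censored when they leave, gave 17.3% and 16.4%. The shortfall therefore comes almost entirely from retaining the withdrawals.

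**The case against.** The best counter-argument is that the direction of the error is not fixed by the text. Overstatement requires deaths to be censored at death, and the plan never says so. A reader might infer that the planned analysis is bound to exaggerate the intervention burden. The documents do not support that, because under the literal rule the bias runs the other way. This stands, and the conclusion has to be conditional.

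The plan also promises curves, and does not say that 1 minus Kaplan-Meier will be reported as a proportion of patients. Kaplan-Meier with deaths censored is still a legitimate description of intervention among patients who remain alive. This stands as a reason to keep the curve. It does not remove the risk that readers take it for the proportion treated.

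Size is a further limit. At 10%, the excess in high-voltage leads is 1.3 points, about 0.3 standard errors even with 65 leads. That lead count uses the maximum reported prevalence. It also belongs with 25.5% mortality only, since no prevalence is given for QuickSite/QuickFlex and the Riata count cannot be paired with 33.7%.

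A reader might also infer that the unequal distortion across lead groups undermines a comparison. Section 3.1 treats each lead group as a separate analysis, and no between-group test of this outcome is planned.

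Finally, the line between a treatment decision and lead reliability is not clean. Section 2.0 defines electrical dysfunction through cases in which the lead was capped, extracted or abandoned. The argument is clearest for sections 3.2.2.7 and 3.2.2.8, where the endpoint is the intervention itself, and the point is confined to them.

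**Conclusion.** The point holds in a limited form. Neither reading of the current text gives the share of patients who undergo an intervention. With deaths censored at death, a reported 20% would correspond to 17.4% at 25.5% mortality or 16.5% at 33.7%. With everyone carried to 3 years, the report would be 16.2% or 15.4%. The choice of reading alone moves the result by 3.8 points at the lower mortality and 4.6 points at the higher.

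These figures rest on constant and independent hazards, an assumed intervention risk, and the plan's group-level mortality from enrollment, which may not match mortality among patients with an imaging finding. They are upper values in that they assume a full 3 years after detection. The outcomes are secondary and descriptive, with no threshold or test attached. This is a minor improvement, and the documents do not support calling Kaplan-Meier invalid here or insisting that it be removed.

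**What to change.** In sections 3.2.2.7 and 3.2.2.8:
- Report the Aalen-Johansen cumulative incidence of clinical intervention, with death without intervention as the competing event.
- Censor withdrawals for other reasons at last follow-up, and patients who complete the study without an intervention at the end of their planned follow-up. Apply the same rule to findings present at enrollment and to later ones.
- Show the cumulative incidence of death without intervention on the same figure.
- If Kaplan-Meier is kept alongside, label it as the estimate with deaths censored.

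No new data are needed, since section 8.0 already requires every death to be reported and asks for its date. The cost is a change of wording, one more curve per figure, and slightly lower reported percentages than Kaplan-Meier with deaths censored would give.

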3.2.2.8 Time from other visual lead anomalies by each subcategory to clinical intervention

Lead Population

All the leads with other visual lead anomalies (by each sub category) within the Riata, Riata ST silicone, QuickSite/QuickFlex (1056T, 1058T, 1156T, 1158), and Durata lead groups

Analysis:

Time to clinical intervention will be analyzed using the Kaplan-Meier method. The zero time will be the date at

which other visual lead anomaly (by each subcategory) was detected. Those patients who experience other visual lead anomaly (by each subcategory) after enrollment but do not experience clinical intervention will be censored 3 years after enrollment in this trial. A separate Kaplan-Meier curve will be calculated for each of the lead subgroups outlined in Table 2.

For QuickSite/QuickFlex leads only, data from patients with an additional 1 year of follow-up will contribute to 2 separate lead subgroups (See Section 3.4.5).

3.2.2.9 Comparison of patients with lead compromise as evidenced by imaging (includes externalized conductors and other visual lead anomalies by each subcategory) to those without lead compromise

Patient Population

All the patients within the Riata, Riata ST silicone, QuickSite/QuickFlex (1056T, 1058T, 1156T, 1158) and Durata lead subgroups.

Analysis

Demographic and clinical parameters will be compared between patients who experience a lead compromise as evidenced by imaging and those who do not experience a lead compromise. Specifically, the variables age, gender, body mass index, lead size, lead model, and implant factors such as venous access site, number of other leads in the vasculature, fixation location in the right ventricle, level of activity (based on functional NYHA class scale I, II, III, IV), level of therapy that patient received (no ATP/shock, ATP or shock) and slack (grades 0, 1, 2, 3, 4 based on the scale described by Ha et al., 2010¹²) in the lead will be used for the comparison. Continuous variables such as age or body mass index will be compared using Student's T-tests while categorical variables such as gender or lead models will be compared using Pearson's Chi-square statistic. Point estimates and p-values will be provided from these analyses.

3.2.2.10 Comparison of patients with electrical dysfunction to those without electrical dysfunction.

Patient Population

All the patients within the Riata, Riata ST silicone, QuickSite/QuickFlex (1056T, 1058T, 1156T, 1158) and Durata lead subgroups.

Analysis

Demographic and clinical parameters will be compared between patients who experience electrical dysfunction and those who do not experience electrical dysfunction. Specifically, the variables age, gender body mass index, lead size, lead model, and implant factors such as venous access site, number of other leads in the vasculature, fixation location in the right ventricle, level of activity (based on functional NYHA class scale I, II, III, IV), level of therapy that patient received (no ATP/shock, ATP or shock) and slack in the lead (grades 0, 1, 2, 3, 4 based on the scale described by Ha et al, 2010¹²) will be used for the comparison. Continuous variables such as age or body mass index will be compared using Student's T-tests while categorical variables such as gender or lead models will be compared using Pearson's Chi-square statistic. Point estimates and p-values will be provided from these analyses.

In addition, the two patient groups will be compared for the following endpoints:

1. Frequency of externalized conductors. This will be done using a Pearson's Chi-square analysis.
2. Frequency of other visual lead anomalies. This will be done using a Pearson's Chi-square analysis.
3. Time to detection of externalized conductors. A Kaplan-Meier analysis will be used for this comparison.
4. Time to detection of other visual lead anomalies. A Kaplan-Meier analysis will be used for this comparison.
5. The extent of externalization will be compared using Pearson's Chi-square analysis.
6. Number of zones with externalization within one lead will be compared using a Student's T-test.
7. Location of externalization will be compared using Pearson's Chi-square analysis.
8. Amount of slack in the lead (based on the scale described by Ha et al, 2010)¹² will be compared using Pearson's Chi-square analysis.

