3.0 Clinical Protocol

3.1 Study Design and Scope

This study is a prospective, non-randomized, multi-center, international post market study that will determine the prevalence and incidence of externalized conductors and other visual lead anomalies (as evidenced by imaging) and the risk of progression to electrical dysfunction in a large series of ICD/ CRT-D/CRT-P devices containing one or more of the following SJM leads: Riata leads, Riata ST silicone leads, Durata leads, QuickSite/QuickFlex CRT leads. A patient that has at least one market released lead implanted in time period indicated in Table 1 is eligible for enrollment in the study. Each lead group will be considered separately for independent analysis.

Table 1: Leads Eligible for Enrollment

Lead Group	Model Numbers	Lead Implant Date
Riata	1560, 1561, 1562, 1570, 1571, 1572, 1580, 1581, 1582, 1590, 1591, 1592	2002-2009
Riata ST Silicone	7000, 7001, 7002, 7010, 7011, 7040, 7041, 7042	2006-2009
QuickSite/QuickFlex	1056T, 1058T, 1156T, 1158T	2006-2010
Durata	7120, 7121, 7122, 7130, 7131, 7120Q, 7121Q, 7122Q, 7170Q, 7171Q, 7172Q	2008-2010

In order to determine the prevalence and incidence of externalized conductors, other visual lead anomalies as well as electrical dysfunction in the population of leads being evaluated, a minimum of 1500 leads listed above will be enrolled at up to 60 sites. This will comprise a minimum of 300 leads in the Riata lead group and a minimum of 200 leads in the Riata ST lead group to make a combined total of at least 500 Riata and Riata ST silicone leads. The study will also include at least 500 leads in the QuickSite/QuickFlex and Durata lead groups. All patients will be followed every six months for three years.

Adequate representation across the different ages of the leads is also needed to understand the lead population being studied. Therefore, the leads from each group of leads will be compromised of subgroups based on the age of lead (at enrollment) being studied. The required minimum enrollment for each subgroup per lead group is indicated in Table 2. Even if the minimum enrollments indicated in Table 2 are met, extra enrollments may be required to ensure a minimum of 500 leads in each lead group.

Expected Attrition in patients with high voltage leads

Withdrawals due to death

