*Expected attrition in each of the lead groups is based on the rationale provided above the table as well as larger attrition expected in older leads.

[figure not shown]
At enrollment, medical history, demographic data and lead measurement data will be collected. Additionally, cinefluoroscopy (AP, LAO 45° or the best possible LAO view, RAO 45° or the best possible RAO view) will be performed to determine the prevalence of lead compromise. A copy of

cinefluoroscopy performed as part of separate screening can be used to determine the prevalence of lead compromise as long as all three views (AP, LAO 45° or the best possible LAO view, RAO 45° or the best possible RAO view) are available. In patients with evidence of externalized conductors or other visual lead anomalies (fracture, subclavian crush, kink, broken filars on a shocking coil and other irregularities) the following chest x-rays or other available imaging studies will be collected (if available): a) earliest imaging study showing evidence of externalized conductors or other visual lead anomaly and b) latest imaging study that does not show any evidence of externalized conductors or other visual lead anomaly

Data will be collected at 6, 12, 18, 24, 30, and 36 months post enrollment and during any unscheduled follow-up visits due to patient symptoms suggestive of or with evidence of lead electrical problems. Additionally, cinefluoroscopy (AP, LAO 45° or the best possible LAO view, RAO 45° or the best possible RAO view) will be performed in all patients to determine the incidence and mechanical progression of externalized conductors at the 12, 24, and 36 month visits.

During any follow-up visits, device data and stored electrograms will be collected. All clinical events such as hospitalizations, emergency room visits, and adverse events will also be collected. All study data, including device data and stored electrograms will be sent to SJM electronically. If any lead being followed in this study develops a significant electrical abnormality suggestive of lead malfunction and x-ray or cinefluoroscopy would be performed as per the site standard of care then copies of x-ray or cinefluoroscopy should be submitted to SJM.

During the course of the study, any explanted leads should be returned to Returned Goods, St Jude Medical, Sylmar, CA, for analysis.

Study Flow Diagram

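### The ever/never comparisons in 3.2.2.9 and 3.2.2.10 leave out age of lead and time at risk, so variables tied to implant era can appear associated with the outcome when they are not

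*Combined protocol and SAP*

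**What the plan says.** Sections 3.2.2.9 and 3.2.2.10 split patients by whether they ever had the outcome. For imaging findings: "Demographic and clinical parameters will be compared between patients who experience a lead compromise as evidenced by imaging and those who do not experience" one. For electrical dysfunction: "Demographic and clinical parameters will be compared between patients who experience electrical dysfunction and those who do not experience electrical dysfunction".

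The list begins "Specifically, the variables age, gender, body mass index, lead size, lead model, and implant factors such as venous access site" and goes on to other implant factors, NYHA class, therapy received and slack. Age stands beside gender and body mass index, so it is patient age. Age of lead and length of follow-up are not listed.

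On method, the rule for measurements is: "Continuous variables such as age or body mass index will be compared using Student's T-tests". The rule for the other variables, given in the same sentence of the plan, is: "categorical variables such as gender or lead models will be compared using Pearson's Chi-square statistic". The output is described so: "Point estimates and p-values will be provided from these analyses". No regression, stratified test or adjustment is specified anywhere in the document.

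Elsewhere the plan treats age of lead as central. Section 3.1 says "Adequate representation across the different ages of the leads is also needed to understand the lead population being studied", Table 2 sets enrollment minimums by age of lead, and its footnote refers to "larger attrition expected in older leads". The hazard rates in 3.2.1.4 to 3.2.1.6 are assessed by those subgroups. The time-to-event measures (3.2.2.1 to 3.2.2.5, 3.2.2.7 and 3.2.2.8) get a separate Kaplan-Meier curve for each. The two comparison sections do neither.

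**The concern.** Suppose the outcome is commoner in older leads. Any listed variable whose distribution shifts with implant year will then differ between the ever and never groups even if it does nothing to the lead. Lead model and lead size are the plausible candidates, because product lines change over the implant years in Table 1.

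The ever/never split also ignores exposure. A patient who dies or leaves after one year without a finding is counted like one followed for three years without a finding. A variable linked to early death or withdrawal can then look mildly protective.

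The unit adds an ambiguity. Both sections define a patient population, but lead size, model, slack and fixation location belong to a lead. Inclusion requires at least one eligible lead, so a patient may carry two, and the text does not say which lead's value is used.

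At stake is how far the reported p-values can be trusted. A reader could not tell an association with the variable from an association with age of lead.

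**Working it through.** **1. The plan's attrition figures.** The sections give no sample size, alpha or effect size for these tests, so the nearest stated figures are those for attrition in Section 3.1. Three-year mortality is 1 − 0.93³ = 19.6% (ICD) and 1 − 0.872³ = 33.7% (the CRT study). The plan's 60:40 mix gives 0.6 × 0.20 + 0.4 × 0.337 = 25.5%. Total attrition is 1 − 0.745 × 0.85 = 36.7% (stated 37%). With the extra 10% for Riata it is 1 − 0.745 × 0.85 × 0.90 = 43.0% (stated 43%). For left ventricular leads it is 1 − 0.663 × 0.85 = 43.6% (stated 43.6%). All three reproduce.

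**2. Lead-age effect, within one lead group.** From Table 2: Riata targets of 195, 185 and 180 leads from the oldest to the youngest band, 560 in total. Assumed, because the documents give neither: outcome prevalence by band, and the share of leads in each band with a binary factor that has no effect.

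One case in full, with outcome 30/22/15% and factor 70/45/20%:
- Leads with the factor: 195 × 0.70 + 185 × 0.45 + 180 × 0.20 = 136.5 + 83.25 + 36 = 255.75. Events among them: 136.5 × 0.30 + 83.25 × 0.22 + 36 × 0.15 = 64.67.
- Leads without it: 58.5 + 101.75 + 144 = 304.25. Events: 58.5 × 0.30 + 101.75 × 0.22 + 144 × 0.15 = 61.54.
- Crude odds ratio: (64.67 / 191.09) / (61.54 / 242.72) = 1.33. Within every band it is 1.

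Rejection rates at a nominal two-sided 5%, from simulated tables, unadjusted Pearson test:

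| Outcome by band | Factor 50/45/40% | Factor 60/45/30% | Factor 70/45/20% |
|---|---|---|---|
| 25/20/15% | OR 1.04, 6% | OR 1.13, 9% | OR 1.23, 17% |
| 30/22/15% | OR 1.06, 6% | OR 1.19, 14% | OR 1.33, 29% |
| 33/20/10% | OR 1.10, 7% | OR 1.32, 27% | OR 1.59, 61% |

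With the factor equally common in all bands, the unadjusted rate is about 5%. A Cochran-Mantel-Haenszel test stratified by Table 2 band gives about 5% in every cell.

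**3. Follow-up effect.** From Section 3.1: annual mortality of 7% and 12.8%, other loss of 15% over three years, cinefluoroscopy at 12, 24 and 36 months. Assumed: the same annual hazard h in both groups. Annual retention is s = (1 − m) × 0.85^(1/3), which is 0.881 at 7% and 0.826 at 12.8%. The proportion ever detected is the sum over k = 1 to 3 of sᵏ(1 − h)ᵏ⁻¹h.
- At h = 0.05: 0.05 × (0.881 + 0.737 + 0.617) = 11.2%, against 0.05 × (0.826 + 0.648 + 0.509) = 9.9%. The ratio is 0.89, and it stays at 0.89 for h from 0.01 to 0.10.
- With continuous detection, h/(h + d) × (1 − e^(−3(h + d))) with d = 0.127 and 0.191 gives 11.6% against 10.7%, ratio 0.92. For 560 leads split 60:40, the false-positive rate is then about 6%.
- If cases present at enrollment count as events (assumed 10% or 20%, h = 0.03), the ratio is 0.96 or 0.98.

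The optional fourth year in Section 3.4.5 works the other way. With 12.8% mortality, four planned years against three give a ratio of 1.18 to 1.22. This arises only inside QuickSite/QuickFlex, and only for variables linked to who is extended.

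**The case against.** Several points on the other side stand.

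- **The large figures need a steep assumption.** A false-positive rate of 17% to 61% requires the factor to shift by 50 percentage points across the age bands. At a 10-point shift the rate is 6% to 7%. Gender, body mass index, venous access and slack have no evident link to implant era, so for them the bias may be close to nil. The outcome gradient is assumed too: the 0.5% to 33.3% range in the Introduction is by lead model, not by lead age.
- **The survival part is small.** A reader might infer that early deaths seriously distort these comparisons. The plan's mortality figures give a ratio of only about 0.9. They also contrast device types, which are not a listed variable, and the documents give no mortality by NYHA class or patient age.
- **The text claims little.** A reader might infer that the plan will publish null variables as risk factors. The sections describe comparisons of patient groups and do not use that term, and none of the eight objectives in Section 2.0 is to identify risk factors. Point estimates are promised beside the p-values; only intervals are missing.
- **Lead families are kept apart.** Section 3.1 says each lead group is analysed separately, which limits mixing across families. It leaves age of lead uncontrolled within a group, and the table above is for one group.
- **Some time-based analysis exists.** Items 3 and 4 of 3.2.2.10 use Kaplan-Meier, but for detection of imaging findings, not for the demographic and clinical variables.

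A further limit is that therapy received may be a consequence of lead failure. Adjusting for age of lead does not cure that.

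**Conclusion.** The gap is real, and nothing elsewhere in the document closes it. The comparisons are unadjusted and ever/never, and they omit both the factor on which enrollment is stratified and time at risk. Null variables tied to implant era can therefore appear associated with lead compromise or electrical dysfunction. The documents do not support saying that they will.

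For the Riata targets and an assumed 30/22/15% outcome gradient, the false-positive rate runs from about 6% through 14% to 29% as the factor's shift across bands grows from 10 to 30 to 50 points, against about 5% after stratification. Where in that range a given variable lies cannot be judged from the documents. Differential follow-up is a minor addition. The number of patients with two study leads is not stated, so the unit problem cannot be sized.

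These are the last two of ten secondary measures. The point is a worthwhile correction at little cost, and it does not touch the primary outcomes.

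**What to change.** In 3.2.2.9 and 3.2.2.10:

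- Make the lead the unit of analysis and work within each lead group. If leads are pooled across groups, use patient-clustered standard errors.
- Stratify or adjust every comparison by age of lead at enrollment, for example Cochran-Mantel-Haenszel by Table 2 band, or logistic regression for cases present at enrollment.
- Analyse new cases separately, with time at risk. For imaging findings, use a discrete-time model at the annual cinefluoroscopy visits, because ordinary Cox regression would ignore that detection happens only at those visits.
- Report estimates with 95% confidence intervals beside the p-values, and label the comparisons descriptive. State that therapy received may follow from lead failure.

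Age of lead and follow-up time are already needed for Table 2 and the Kaplan-Meier analyses, so no new data are required. The cost is revised wording, modest programming and slightly wider intervals.
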